4.5 Study completion status (end of study)

A patient has **completed the study** after he/she has been followed for 28 days:

1. After having either prematurely discontinued pasireotide s.c.
2. Or, after completing treatment as per protocol (*i.e.* when the study drug is approved for commercial use and reimbursed in each respective country or until 31 December 2015 and until 31 December 2016 for sites in South Korea and Brazil, whichever occurs first).

4.6 Analysis sets

4.6.1 Full analysis set

The Full Analysis Set (FAS) comprises all patients who received at least one dose of pasireotide s.c.

4.6.2 Safety set

The safety set includes all patients who received at least one dose of pasireotide s.c. and had at least one post-baseline safety assessment amongst the following parameters: adverse events, laboratory assessments, vital signs, and ECG.

Please note: the statement that a patient had no adverse events (on the Adverse Event CRF) constitutes a safety assessment.

4.7 Subgroups

Subgroups are based on characteristics measured before study inclusion. Subgroup analyses are described in [Section 6](#).

4.8 Study drug exposure

Duration of exposure (in weeks) will be calculated as

- $$\text{Duration of exposure} = (\text{study drug end date} - \text{study drug start date} + 1) / 7 \text{ days}$$

The exposure duration includes periods of temporary interruption for any reason.

4.9 Calculation of change

Baseline value is the value collected during the baseline assessment as per the specific definition applying to the parameter, e.g. lab value

Absolute change from baseline is the absolute difference between value at time point t (post-baseline) and value at baseline assessment, it is calculated as:

- $Absolute\ change\ from\ baseline = post-baseline\ value - baseline\ value$

Relative change from baseline, or Percentage change from baseline, is calculated as:

- $Relative\ change\ from\ baseline\ (\%) = (absolute\ change\ / baseline\ value) \times 100$

4.10 Dose calculations

Total daily dose

The **total daily dose** is the sum of the evening and morning dose:

$$Total\ daily\ dose\ (\mu g\ / day) = morning\ dose\ (\mu g) + evening\ dose\ (\mu g)$$

Cumulative dose

The **cumulative dose** (μg) is defined as the total dose administered to a patient over the whole study period.

$$Cumulative\ dose\ (\mu g) = \sum (morning\ dose_i + evening\ dose_i)$$

Where i is the day and morning and evening doses are being expressed in μg .

Mean daily dose

Mean daily dose or dose intensity (DI) is defined as:

$$DI\ (\mu g/day) = Cumulative\ dose\ (\mu g) / Duration\ of\ exposure\ (days).$$

For patients who did not take any drug the mean daily dose is by definition equal to zero.

Similarly, a **4-week mean daily dose** will be computed over a 4-week period in order to allow exploratory analyses on the impact of the dose on clinical safety (adverse events).

Mean daily dose grouping

Mean daily dose category is defined on the mean daily dose considering the following grouping rule:

- **600 μg bid group** includes all patients whose mean daily dose $< 1500\ \mu g\ / day$.
- **900 μg bid group** includes all patients whose mean daily dose $\geq 1500\ \mu g\ / day$

Note: As mean daily dose groups are based on the actual exposure to the treatment, i.e. not considering days without any study drug administration, reflecting an actual dosing rather than the intended one. That is, 0 dose days are not considered for mean daily dose grouping.

4.10.1 Sample size calculation

No sample size calculation was performed. The planned sample size of approximately 200 patients was chosen based on the expected accrual rates and the planned duration of the trial. The actual sample size may differ from this planned number.

4.11 Analyses

4.11.1 Interim report

It was anticipated that the timing of drug approvals would differ between regions leading to different study completion amongst the different regions (e.g. EU and non-EU sites). Therefore, data from a specific region may have to be reported when all patients from that region have completed the trial.

The primary reason for those analyses are to address health authorities' needs and/or requests, for this reason, data from other regions may be considered in the analysis planned for one region even if the study is still ongoing. Furthermore, independent of a regional interim analysis additional interim analysis may be performed for regulatory purpose or publication purpose and details will be specified in the study's analysis plan.

Note that this is not a formal interim analysis and does not affect any statistical tests as no hypothesis testing is planned.

4.11.2 Final analysis

The final analysis will be performed when all patients have completed the study.

4.12 Methods for calculating confidence intervals (CI)

4.12.1.1 CI for proportions

Two-sided 95% confidence intervals for proportions will be calculated on the exact method. Confidence intervals will be obtained using Clopper-Pearson confidence intervals ([Clopper and Pearson 1934](#)).

4.12.1.2 CI for continuous variables

Two sided 95%Confidence Interval for continuous variable will be based on the t-distribution. The respective N, Mean and Standard error are outputted in to a data-step and then the TINV function is used to calculate the Confidence Interval as follows:

```
PROC MEANS DATA=test NOPRINT ;
  VAR age ;
  OUTPUT OUT=xxtmp N=n MEAN=mean STDERR=stderr ;
  RUN ;

  DATA xxtmp1 ; SET xxtmp ;
  lo = mean - ( TINV ( 0.95 , n-1 ) * stderr ) ;
  hi = mean + ( TINV ( 0.95 , n-1 ) * stderr ) ;
  RUN ;
```

5 Statistical methods and data analysis

Categorical data will be presented as frequencies and percentages. For continuous data, mean, standard deviation, median, minimum, and maximum will be presented.

A missing category for categorical data will be presented where applicable. Unless otherwise noted, percentages will be based on the number of patients in the relevant population or subgroup.

Whenever possible, minimum and maximum will be presented to the same precision as the raw data. Mean and median will be presented to one more decimal place and standard deviation to two more decimal places.

Unless noted otherwise, no imputation for missing data will be performed.

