10.5.1 Secondary efficacy variables

The secondary efficacy analysis will be performed on the FAS. Unless noted otherwise, missing values will not be imputed in these analyses. The parameters assessed at screening and not at baseline are to be considered as baseline.

10.5.1.1 Normalization of mean 24h-UFC at Week 12, 24 and 48

The number and percentage with corresponding exact two-sided 95% CI of patients achieving normalization of mean 24h-UFC (i.e. mean 24h-UFC \leq 1.0xULN) at Week 12, 24 and 48 (separately) will be presented.

If Week 24 mean 24h-UFC is missing then it will be imputed by the last available mean 24h-UFC of at least two samples between and including Week 12 and Week 24, and if Week 48 mean 24h-UFC is missing then it will be imputed by the last available mean 24h-UFC of at least two samples between and including Week 12 and Week 48. Summaries with and without imputing missing Week 24 and Week 48 mean 24h-UFC will be presented.

Similar analyses as defined above will also be performed at all other scheduled post-baseline assessments.

10.5.1.2 Reduction of mean 24h-UFC \geq 50% from baseline to Week 12, 24 and 48

The number and percentage with corresponding exact two-sided 95% CI of patients achieving a reduction of mean 24h-UFC \geq 50% from baseline to Week 12, 24 and 48 (separately) will be presented.

Similar analyses as defined above will also be performed at all other scheduled post-baseline assessments.

10.5.1.3 Change from baseline in mean 24h-UFC to Week 12, 24 and 48

Descriptive summaries of actual and percentage change with corresponding two-sided 95% CIs in mean 24h-UFC from baseline to Week 12, 24 and 48 will be provided.

Similar analyses as defined above will also be performed at all other scheduled post-baseline assessments.

10.5.1.4 Changes from baseline in GH and IGF-I to Week 12, 24 and 48

Descriptive summaries of actual and percentage change in mean GH and IGF-1 values from baseline to Week 12, 24 and 48 will be provided.

Similar analyses as defined above will also be performed at all other scheduled post-baseline assessments.

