Version	Date	Changes
2.0	11-Nov-2011	Initial version
2.1	13-June-2012	
Biomarker section modified: Hscores for Immunohistochemistry added
 
Incorporation of changes made after Protocol amendment 3
 
Objectives and Endpoints
 
As a consequence of extending the study duration, objectives and endpoints have been updated to include an additional time point for analysis at week 48.
 
Description of Study Design
 
This section has been updated to reflect the changes of the starting dose in the European Union and the change of study duration.
 
Subgroup analysis
 
In this section an additional analysis by starting dose has been added.
 
(Adding week 48, starting dose)

2.2	22-July-2012	Revision after 2 nd RAP II meeting (visit windows, dose calculation, biomarker section)
3.0	26-Sep-2012	
Final version, Amendment 1
 
Revision after LF review
 
Mean daily dose grouping has been added.
 
Section 4.4 Visit window has been added.
 
Section 4.9 Calculation of changes has been added.
 
Section 4.10 Dose calculations has been added
 
Section 4.12.1.2 CI for continuous variable has been added.

3.1	26- Oct -2012	Removed “Normally Distributed” from section 4.12.1.2
3.2	29-Sep-2016	
Draft version , Amendment 2
 
Added Mean 24h-UFC calculation section: the mean UFC calculation at week 12,24and 48 will be based on the last two or three samples collected before the visit , instead of considering only three samples
 
Update sample size calculation
 
Added the publication purposes in the interim analysis
 
Removed biomarker data analysis due to the fact that the vendor never analyzed the data collected for only 7 patients due to Novartis decision

3.3	10-Mar-2017	Final version , Amendment 2

1 Introduction

The RAP document describes the planned statistical analyses for the clinical study report for study SOM230B2406 in the treatment of Cushing's disease. SAS® version 9.4 (SAS Institute Inc., Cary, NC, USA) or later will be used for all analyses. Any changes made to this statistical plan after the clinical database lock will be documented separately.

Even written before database lock, this document is using past tense in order to simplify the CSR writing.

2 Study design and treatment

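### The SAP's code for continuous-variable confidence intervals uses the 0.95 t quantile on both sides, so intervals labelled two-sided 95% are 90% intervals

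*SAP*

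**What the plan says.** SAP section 4.12.1.2 sets the level and the distribution: "Two sided 95%Confidence Interval for continuous variable will be based on the t-distribution". It then gives the SAS code by which the interval is to be calculated. The sample size, mean and standard error come straight from PROC MEANS ("OUTPUT OUT=xxtmp N=n MEAN=mean STDERR=stderr"), and the limits are formed as "lo = mean - ( TINV ( 0.95 , n-1 ) * stderr" and "hi = mean + ( TINV ( 0.95 , n-1 ) * stderr". The SAP introduction names SAS version 9.4 or later, which "will be used for all analyses".

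On the protocol side, section 10.5.1.3 asks for "Descriptive summaries of actual and percentage change with corresponding two-sided 95% CIs in mean 24h-UFC" from baseline to Weeks 12, 24 and 48, with similar analyses at the other scheduled post-baseline assessments.

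Proportions have their own rule in SAP section 4.12.1.1: "Two-sided 95% confidence intervals for proportions will be calculated on the exact method", using Clopper-Pearson limits.

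**The concern.** A symmetric two-sided 95% interval leaves 2.5% in each tail and so needs the 0.975 quantile of the t distribution. The code uses the 0.95 quantile for both limits. The section therefore states one confidence level in its text and codes another.

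At stake is the uncertainty reported around the change in urinary free cortisol. The study has one arm and tests no hypotheses (Protocol section 10.4.2), so readers have only the interval to judge how precisely a mean change is estimated. If the code is followed, the interval misses the true mean 10% of the time under a label that promises 5%. SAP section 4.11.1 also allows interim reports for regulatory or publication purposes, so the same code could feed more than one report.

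**Working it through.** **Inputs**
- Stated level: two-sided 95%, so 0.025 per tail (SAP 4.12.1.2).
- Coded multiplier: `TINV(0.95, n-1)` for both limits (SAP 4.12.1.2).
- Standard error: `STDERR` from PROC MEANS, with no rescaling that could compensate (SAP 4.12.1.2).
- Software: SAS (SAP section 1). The documents do not define `TINV`; the standard SAS definition is used, under which it returns the lower-tail quantile.
- Sample size: about 200 planned (SAP 4.10.1, Protocol 10.8). Smaller values stand for visits or subgroups with fewer patients and are illustrative.

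**Formula.** For limits mean ± q × stderr, two-sided coverage is 2 × F(q; n-1) - 1, where F is the cumulative t distribution.

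**Can the stated 95% be reproduced from the code?** With q equal to the 0.95 quantile, F(q) = 0.95 by definition, so coverage = 2 × 0.95 - 1 = 0.90, whatever n is. The stated 95% does not reproduce. With the 0.975 quantile, coverage = 2 × 0.975 - 1 = 0.95, and it does.

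**Size of the error**

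| n | Multiplier as coded | Multiplier for 95% | Coded interval too narrow by | Correct interval wider by |
|---|---|---|---|---|
| 10 | 1.8331 | 2.2622 | 19.0% | 23.4% |
| 20 | 1.7291 | 2.0930 | 17.4% | 21.0% |
| 50 | 1.6766 | 2.0096 | 16.6% | 19.9% |
| 100 | 1.6604 | 1.9842 | 16.3% | 19.5% |
| 200 | 1.6525 | 1.9720 | 16.2% | 19.3% |

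For n = 200: 1 - 1.6525/1.9720 = 0.162, and 1.9720/1.6525 - 1 = 0.193.

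**Simulation check.** In 100,000 samples of normal data at each size, coverage was:
- as coded: 0.8996 at n = 50 and 0.9003 at n = 200;
- with 0.975: 0.9500 at n = 50 and 0.9498 at n = 200.

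**Alternative readings**
- One-sided bounds: the same quantile is both subtracted and added, and the text says two-sided, so the pair is an interval.
- Argument read as a two-tailed probability, as some spreadsheet functions do: at n = 200 the multiplier would be 0.0628 and coverage 5%, further from 95%.
- A correction elsewhere: neither document gives another multiplier for continuous variables.

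**The case against.** No passage corrects the multiplier, so the case on the other side concerns reach and weight.

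- **Most of the study's intervals are untouched.** UFC normalization, the 50% reduction and the clinical-sign thresholds are proportions with exact intervals. This stands; the finding covers only t-based intervals for continuous variables.
- **Few outputs call for such an interval.** Protocol 10.5.1.3 is the only place found that explicitly asks for one. The matching text in SAP section 5.2.1 describes the change in mean 24h-UFC without an interval, and the GH/IGF-I, CushingQoL and WPAI-GH summaries mention none. Nor is the change in mean 24h-UFC a listed endpoint in Protocol Table 3-1; both UFC endpoints there are proportions. This also stands and limits the reach. It does not remove the error: the protocol requires the interval, and SAP 4.12.1.2 is the only method specified for it.
- **Nothing is decided on these intervals.** No hypothesis is tested, no sample size calculation was made, and the primary variable is a proportion. This stands and makes the harm descriptive.
- **The code is a template.** Its example variable is `age` and its dataset is called `test`; the production programs cannot be seen. So it cannot be said that reported intervals are wrong, only that the specified method contradicts its stated level. But the SAP presents the code as the way to calculate the interval. If the production programs already use 0.975, the SAP misdescribes the analysis and still needs correcting.

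**Conclusion.** The concern holds. As written, SAP 4.12.1.2 specifies a 90% interval and calls it 95%. The nominal miss rate doubles from 5% to 10%, and the interval is 16.2% too narrow at n = 200 and 17.4% too narrow at n = 20.

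This rests on the standard SAS meaning of `TINV` and on the template being followed. The coverage figures are exact for normally distributed data. With skewed data, the actual coverage of both versions may differ from nominal, but the width ratios are unchanged.

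The error is confined to t-based intervals for continuous variables, chiefly the descriptive summaries of change in mean 24h-UFC. The primary result, the responder proportions and the sample size are unaffected.

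**What to change.** In SAP 4.12.1.2, replace 0.95 with 0.975 (or 1 - 0.05/2) in both the `lo` and the `hi` line. Alternatively, drop the hand calculation and take the confidence limits directly from PROC MEANS with ALPHA=0.05. Check any production program or interim output built on the template, and rerun it where 0.95 was used.

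In the same revision, state in SAP section 5.2.1 that the change in mean 24h-UFC is reported with a two-sided 95% interval, so that it matches Protocol 10.5.1.3.

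The cost is an edit to two lines of code and one sentence of text, plus reruns if needed. No new data are required and no design element changes. The corrected intervals are 19.3% wider at n = 200 and 21.0% wider at n = 20.

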11.5 Publication of study protocol and results

Novartis assures that the key design elements of this protocol will be posted in a publicly accessible database such as clinicaltrials.gov. In addition, upon study completion and finalization of the study report the results of this study will be either submitted for publication and/or posted in a publicly accessible database of clinical study results. Different publications of the data are planned. Regional and/or country population analysis and publication will be allowed after the analysis and presentation of the multinational (or global) population is performed.

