This study is an open-label, uncontrolled, single-arm, multi-center, multi-national expanded access study of pasireotide sub-cutaneous administered twice a day in patients with persistent or recurrent Cushing's disease or with de novo Cushing's disease that are not considered candidates for pituitary surgery (confirmed Cushing's disease).

The starting dose depends on the location of the site:

For sites located in the European Union: the starting dose is 600 µg b.i.d. . However, patients already enrolled in the study at the time of the approval of the amendment 3 are to continue on their current assigned dose.

For site located outside the European Union: the starting dose is 900 µg b.i.d. in all patients except for those with impaired glucose metabolism for whom the starting dose is 600 µg b.i.d.

After a 21-day screening period, patients who satisfied all the inclusion/exclusion criteria started receiving pasireotide. During the first 24-week period, patients had a visit on a weekly basis up to week 4 and then on a 4-week basis. In the second study period, i.e. after the 24 week visit, visits are taking place on 12-week intervals until the end of the study.

Patients remained in the study until pasireotide is approved for commercial use and reimbursed in each respective country or until 31 December -2015 (until 31 December 2016 for sites in South Korea and Brazil), whichever occurred first.

3 Objectives

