4.4 Visit windows

It is anticipated that some assessments could be done outside the protocol planned visit windows, for that purpose a computed Visit windows schedule is defined.

Visits after the date of first dose are scheduled weekly for the first 4 weeks and then monthly from study day 28 (visit number 6) to study day 168 (visit number 11). Thereafter every 12 weeks/84 days.

Table 4-1 Visit windows

Study visit	Week	Visit window	Visit window Start*	Visit window Mid-point*	Visit window End*	Visit window Duration
1 (Screening)	-1	-1	-21	0	-1	21
2 (Baseline)	0	0	0	0	0	1
3	1	1	1	7	11	7
4	2	2	12	14	18	7
5	3	3	19	21	25	7
6	4	4	26	28	32	7
7	8	5	33	56	70	28
8	12	6	71	84	98	28
9	16	7	99	112	126	28
10	20	8	127	140	154	28
11	24	9	155	168	182	28
12	36	10	183	252	294	84
13	48	11	295	336	378	84
14	60	12	379	420	462	84
15	72	13	463	504	546	84
16	84	14	547	588	630	84
17	96	15	631	672	714	84
18	108	16	715	756	798	84
19	120	17	799	840	882	84
20	132	18	883	924	966	84
21	144	19	967	1008	1050	84
22	156	20	1051	1092	1134	84

*Note: * study day*

For summary statistics (tables) for all laboratory data assessment visits are processed as follows:

1. Unscheduled visits are used.

2. Unless stated otherwise, the closest assessment to the mid-point of each visit-window is considered.
3. In case 2 or more assessments are reported on the same day, or have the same distance from the mid-point, i.e. 2 days before, 2 days after, then the mean will be taken.

With regard to mean 24h-UFC, the above rules do not apply as per protocol there are particular definitions, see section 5.2.1 for further details.

All lab assessments are listed.

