5.1.1 Primary variable

The primary variable is the proportion of patients having a drug-related adverse event that was recorded as grade 3 or 4, or as a serious adverse event (see [Section on Adverse events](#) as to how the primary variable will be analyzed).

The analysis will be performed on the Safety set.

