5.3 Safety analyses

5.3.1 Analysis set and grouping for the analyses

For all safety analyses, the safety set will be used.

The overall observation period will be divided into three mutually exclusive segments:

1. Pre-treatment period: from day of patient's informed consent to the day before first dose of study medication,
2. On-treatment period: from day of first dose of study medication to 28 days after last dose of study medication,
3. Post-treatment period: starting at 29 days after last dose of study medication.

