5.3.2 Adverse events

Summary tables for adverse events (AEs) will include only AEs that started or worsened during the on-treatment period, the **treatment-emergent** AEs. However, all safety data (including those from the pre and post-treatment periods) will be listed and those collected during the pre and post-treatment period will be flagged.

For the primary objective of the study, the number and percentage of patients having any drug-related adverse event that was recorded as grade 3 or 4, or as a serious adverse event will be summarized by system organ class and/or preferred term, severity (based on CTCAE grades), and type of adverse event.

In addition, the incidence of treatment-emergent adverse events (new or worsening from baseline) will be summarized by system organ class and/or preferred term, severity (based on CTCAE grades), type of adverse event and relation to study treatment. Deaths will be listed and summarized by cause of death.

The following adverse event summaries will be provided:

- Adverse events, suspected to be study drug related that was recorded as grade 3 or 4, or as a serious adverse event, by primary system organ class and/or preferred term and severity (based on CTCAE grades),

- Adverse events, regardless of study drug relationship, by primary system organ class and preferred term,
- Adverse events, suspected to be study drug related, by primary system organ class and preferred term,
- CTC grade 3 or 4 adverse events, regardless of study drug relationship, by primary system organ class and preferred term,
- CTC grade 3 or 4 adverse events, suspected to be study drug related, by primary system organ class and preferred term,
- Adverse events leading to study drug discontinuation, regardless of study drug relationship, by primary system organ class and preferred term,
- Deaths by primary system organ class and preferred term,
- SAEs, regardless of study drug relationship, by primary system organ class and preferred term,
- SAEs, suspected to be study drug related, by primary system organ class and preferred term,
- SAEs leading to study drug discontinuation, regardless of study drug relationship, by primary system organ class and preferred term.

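### The crude primary adverse-event proportion and the unimputed UFC percentages depend on how long patients happened to be followed, and the visible plan adds neither a fixed-time AE summary nor a UFC base that sets administrative completers apart.

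*SAP*

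**What the plan says.** **Length of follow-up.** SAP Section 2: "Patients remained in the study until pasireotide is approved for commercial use and reimbursed in each respective country", or until 31 December 2015 (2016 for South Korea and Brazil), whichever came first. No minimum is stated. Visits after Week 24 are spaced widely ("Thereafter every 12 weeks/84 days", SAP 4.4), and the visit-window table runs to Week 156. Under Protocol 6.2.2, patients moved to commercial drug, or treated to the cap, count as completed.

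**Primary variable.** SAP 5.1.1: "The primary variable is the proportion of patients having a drug-related adverse event that was recorded as grade 3 or 4", or as serious. SAP 5.3.2: "Summary tables for adverse events (AEs) will include only AEs that started or worsened during the on-treatment period". SAP 5.3.1 defines that period: "On-treatment period: from day of first dose of study medication to 28 days after last dose of study medication". Protocol 10.4.3 and 10.4.4 mark censoring rules and supportive analyses for the primary objective as not applicable.

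**UFC percentages.** SAP 5.2.1 uses the FAS, which requires only one dose (SAP 4.6.1). SAP Section 5 sets the default base: "percentages will be based on the number of patients in the relevant population or subgroup". It also provides a missing category where applicable, with no split by reason. A missing Week 24 or Week 48 mean can be carried forward from Week 12 onward, and results are shown with and without this.

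**Regional reports.** SAP 4.11.1: "data from a specific region may have to be reported when all patients from that region have completed the trial".

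**The concern.** The AE window opens at first dose and closes 28 days after last dose, so its length is set by enrolment date and by the country's approval and reimbursement date. The efficacy endpoints are tied to Weeks 12, 24 and 48; the primary safety endpoint is tied to no time. A percentage with no time frame cannot be set beside that of another regional report, or of a study of fixed length, without knowing how follow-up differs.

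In the unimputed UFC tables, a patient moved to commercial drug before Week 48 is handled like one who dropped out: in the denominator, never in the numerator. Response could then appear to fall across visits simply because countries obtained the drug. With no hypothesis tests, these estimates are the study's main output, so their meaning matters.

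**Working it through.** The plan states no event rate, response rate, power or follow-up distribution; about 200 patients is an accrual choice (SAP 4.10.1). There is no stated figure to reproduce. Every rate below is assumed.

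**1. Primary proportion.** Risk by day *t* is 1 − exp(−H(t)), with hazards per 365.25 days. Two hypothetical reports have identical risk. Treatment time is spread evenly over 4-48 weeks (28-336 days) in one and over 4-156 weeks (28-1092 days) in the other. Each patient has the 28-day tail.

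For constant hazard h, the expected crude proportion over treatment times a to b is

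1 − [exp(−h(a+28)) − exp(−h(b+28))] / [h(b−a)].

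At 0.3/year:
- 4-48 weeks: 1 − (0.9550 − 0.7416)/0.2530 = 15.6%
- 4-156 weeks: 1 − (0.9550 − 0.3986)/0.8739 = 36.3%

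The front-loaded cases keep the same 48-week cumulative hazard and change at day 168: 0.45 then 0.15/year puts 75% of it in the first 24 weeks, and 0.54 then 0.06/year puts 90% there. The rate is mean risk divided by mean event-free time at risk.

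| Hazard | Crude, 4-48 wk | Crude, 4-156 wk | Ratio | Risk by Week 24, both reports | Rate per 100 patient-years |
|---|---|---|---|---|---|
| Constant 0.3/year | 15.6% | 36.3% | 2.3 | 12.9% | 30.0 and 30.0 |
| 75% in first 24 wk | 18.6% | 30.6% | 1.6 | 18.7% | 36.9 and 24.7 |
| 90% in first 24 wk | 20.3% | 26.5% | 1.3 | 22.0% | 41.2 and 21.0 |

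At constant 0.2 and 0.4/year the crude pairs are 10.8% and 26.5%, and 20.2% and 44.5%. Only the fixed-week risk is the same in both reports in every row. The patient-year rate agrees only under constant hazard, so it should be secondary.

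**2. UFC base.** If a share s of the FAS completes administratively before a visit and the response rate among the rest is r, the unimputed FAS percentage is r(1 − s). With 200 patients and r = 30%:

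| s | FAS base (95% CI) | Administrative completers removed (95% CI) |
|---|---|---|
| 10% | 54/200 = 27.0% (21.0-33.7) | 54/180 = 30.0% (23.4-37.3) |
| 25% | 45/200 = 22.5% (16.9-28.9) | 45/150 = 30.0% (22.8-38.0) |
| 50% | 30/200 = 15.0% (10.4-20.7) | 30/100 = 30.0% (21.2-40.0) |

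Intervals are Clopper-Pearson. A mixed case: 60 of 200 complete administratively before Week 48, 40 stop for other reasons, and 37 of the remaining 100 respond. The FAS base gives 37/200 = 18.5% (13.4-24.6). Removing the 60 and keeping the 40 as non-responders gives 37/140 = 26.4% (19.3-34.5).

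**3. Reach of the carry-forward.** It covers Weeks 24 and 48, not Week 12. Protocol 10.5.1.1 places it inside the normalization analysis, and Protocol 10.5.1 says missing values are otherwise not imputed. SAP 5.2.1 gives it its own heading and imputes the mean UFC value, which could feed the ≥50% reduction endpoint too. The documents leave this open.

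**The case against.** The study only documents safety, tests nothing, and plans no comparison between regions. A crude treatment-emergent proportion beside a summary of exposure duration (SAP 5.6) is a legitimate description for an expanded access study. **This stands** as far as validity goes: nothing planned is wrong, and the change is an addition. It does not supply a time frame, because a separate exposure table does not yield risk by a given week. Protocol 11.5 says "Regional and/or country population analysis and publication will be allowed after the analysis and presentation of the multinational (or global) population is performed"; that fixes the order of publication, not the follow-up mix.

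For UFC, the missing category and the imputed summaries already help. **This stands in part.** If missing counts are shown, a reader can rebuild an observed-case percentage, but cannot separate administrative completion from dropout.

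The final SAP is dated 10 March 2017, after the last treatment cap, so new denominators would be defined late in an open-label study. **This stands** and favours a simple rule based on the recorded reason.

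Two stronger readings are tempting. A reader might infer that the plan contains no time-adjusted AE analysis anywhere. SAP Section 6 and Protocol 10.6 are not shown, so only the visible text can be judged; the 4-week mean daily dose in SAP 4.10 links dose to AEs and does not fill the gap. A reader might also infer that carry-forward definitely excludes the ≥50% reduction endpoint. The two documents leave that unclear.

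**Conclusion.** The point holds as a matter of interpretation. That both estimates depend on the follow-up mix follows directly from the design; how strongly does not.

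- **AE proportion:** in the illustrations, two reports with identical risk differ by a ratio of 1.3 to 2.3 across the three hazard shapes at the same 48-week risk. This rests on assumed hazards and on an assumed 4-48 against 4-156 week contrast. A reader might be drawn to set everyone treated for 156 weeks against everyone treated for 12. That describes no plausible pair of reports and should not be used to size the problem.
- **UFC:** an assumed 30% response shows as 27.0%, 22.5% or 15.0% when 10%, 25% or 50% complete administratively before the visit. This assumes completers would have responded like the rest. It applies to unimputed tables; carry-forward offsets it in part for normalization at Weeks 24 and 48.

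It would be wrong to infer that a test, error rate or power is affected: Protocol 10.4.2 tests no hypothesis and SAP 4.10.1 makes no sample size calculation.

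**What to change.** In the SAP only; every planned table stays.

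1. **Primary variable (SAP 5.1.1 and 5.3.2).** Show the crude proportion with the Clopper-Pearson 95% CI of SAP 4.12.1.1. Add cumulative incidence of the first primary event by Weeks 12, 24 and 48, censored at the end of the on-treatment period. Give patients with a first event per 100 patient-years at risk as secondary. State that withdrawal for non-administrative reasons may be informative.
2. **UFC (SAP 5.2.1).** At each visit, split missing values into administrative completion (moved to commercial drug, or reached the cap) and other reasons. Use the reason collected at study phase completion (Protocol 7.1.3), not the completion status in SAP 4.5, which also covers premature discontinuation. Add normalization and ≥50% reduction percentages with patients who completed administratively before the visit removed from the denominator and other missing patients counted as non-responders. Show the denominator at each visit.
3. **Carry-forward.** State whether the Week 24/48 rule applies to the ≥50% reduction endpoint.

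If the database is already locked, record the additions separately, as SAP Section 1 provides.

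**Cost.** Two or three SAP paragraphs and a few tables, from dates and reasons already collected. UFC denominators will vary by visit. Early stoppers whose visit might never have fallen due stay in the denominator, which is conservative. In the mixed case, if the same share of the 40 stoppers as of the other patients (60/160 = 37.5%, so 15) would not have reached Week 48, 26.4% would be 37/125 = 29.6%. That 3.2-point shift is smaller than the 7.9 points (26.4 − 18.5) that the new base removes.
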